## 9.4 Renal safety monitoring

Renal events are defined as one of the following:

- confirmed (after ≥ 24h) increase in serum creatinine of ≥ 25% compared to baseline during normal hydration status
- new onset (≥1+) proteinuria, hematuria or glucosuria; or as a
- doubling in the urinary albumin-creatinine ratio (ACR) or urinary protein-creatinine ratio (PCR) (if applicable).

The following two categories of abnormalities/adverse events have to be considered during the course of the study:

- serum creatinine triggers that will require follow up and repeat assessments of the abnormal laboratory parameter
- urine dipstick triggers that will require follow up and repeat assessments of the abnormal laboratory parameter

**Table 9-3 Specific Renal Alert Criteria and Actions**

Renal Event	Actions
Serum creatinine increase 25 – 49% compared to baseline	Confirm 25% increase after 24-48h Follow up within 2-5 days
Serum creatinine increase $\geq$ 50 % compared to baseline	Follow up within 24-48h if possible Consider drug interruption Consider patient hospitalization /specialized treatment
Albumin- or Protein-creatinine ratio increase $\geq$ 2-fold	Confirm value after 24-48h Perform urine microscopy
Albumin-creatinine ratio (ACR) $\geq$ 30 mg/g or $\geq$ 3 mg/mmol; New dipstick proteinuria $\geq$ 1+	Consider drug interruption / discontinuation
Protein-creatinine ratio (PCR) $\geq$ 150 mg/g or $>$ 15 mg/mmol	
New dipstick glucosuria $\geq$ 1+ not due to diabetes	Blood glucose (fasting) Perform serum creatinine, ACR
New dipstick hematuria not due to trauma	Urine sediment microscopy Perform serum creatinine, ACR
Document contributing factors: co-medication, other co-morbid conditions, and additional diagnostic procedures performed in the CRF	
Monitor patient regularly (frequency at investigator's discretion) until one of the following:	
Event resolution: (sCr within 10% of baseline or protein-creatinine ratio within 50% of baseline)	
Event stabilization: sCr level with $\pm$ 10% variability over last 6 months or protein-creatinine ratio stabilization at a new level with $\pm$ 50% variability over last 6 months.	

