## 7 Discontinuation and study completion

### 7.1 Discontinuation of study treatment

Patients may voluntarily discontinue the study treatment for any reason at any time.

The Investigator should discontinue study treatment for a given patient if, on balance, he/she believes that continuation would be detrimental to the subject's well-being.

- Study treatment **must** be discontinued and patients followed up for safety, if possible, if the following occur:
- In case of non-detectable AChR or MuSK autoantibodies for patients enrolled prior to this amendment.
- Significant increase in MG disease activity requiring treatment outside of a clinical trial setting.
- Worsening of MG with severe oropharyngeal or respiratory weakness (MGFA class IVb or V).
- Rescue medication use (IVIg or plasma exchange).
- Pregnancy.
- Severe or life threatening infusion reaction.
- Major worsening of renal function (e.g. >40% increase from baseline creatinine level).
- Acute infection as a severe AE as judged by the investigator.
- Major elevations (>4.0 x ULN) in amylase or lipase or any abnormal signs or symptoms suggesting pancreatic injury.
- Significant changes in standard coagulation parameters, including prothrombin time (PT), activated partial thromboplastin time (aPTT) suggesting an increased risk for hypercoagulability or any sign or symptom of a TE.
- Any other AE or complication where continued dosing of the patient is considered to be placing them at excess risk.
- Patient withdraws consent (when patient must also be withdrawn from the study).

Patients who are withdrawn from the study for any reason will not be replaced.

Study patients who discontinue participation for any reason or who decide they do not wish to participate in the study further should not be considered withdrawn from the study unless they withdraw their consent (see [Section 7.3](#)). Where possible, they should return for their EoS visit assessments (Visit 777). If they fail to return for these assessments for unknown reasons, every effort (e.g. telephone, e-mail, letter) should be made to contact them as specified in [Section 7.2.1](#). Any unresolved AEs will be followed by the investigator until resolution.

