#### **For the liver events:**

- Repeating the LFT to confirm elevation as appropriate
- Discontinuation of the investigational drug (refer to [Section 7.1](#), if appropriate)
- Hospitalization of the subject if appropriate
- A causality assessment of the liver event via exclusion of alternative causes (e.g. disease, co-medications)
- An investigation of the liver event which needs to be followed until resolution.

These investigations can include serology tests, imaging and pathology assessments, hepatologist's consultancy, based on investigator's discretion. All follow-up information, and the procedures performed should be recorded as appropriate in the CRF, including the liver event overview CRF pages.

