**Table 9-2 Follow Up Requirements for Liver Events and Laboratory Triggers**

Criteria	Actions required	Follow-up monitoring
Potential Hy's Law case a	Discontinue the study drug immediately Hospitalize, if clinically appropriate Establish causality Complete liver CRF	ALT, AST, TBL, Alb, PT/INR, ALP and γGT until resolution c (frequency at investigator discretion)
ALT or AST > 8 × ULN	Discontinue the study drug immediately Hospitalize if clinically appropriate Establish causality Complete liver CRF	ALT, AST, TBL, Alb, PT/INR, ALP and γGT until resolution c (frequency at investigator discretion)
> 3 × ULN and INR > 1.5	Discontinue the study drug immediately Hospitalize, if clinically appropriate Establish causality Complete liver CRF	ALT, AST, TBL, Alb, PT/INR, ALP and γGT until resolution c (frequency at investigator discretion)
> 5 to ≤ 8 × ULN	Repeat LFT within 48 hours If elevation persists, continue follow-up monitoring If elevation persists for more than 2 weeks , discontinue the study drug Establish causality Complete liver CRF	ALT, AST, TBL, Alb, PT/INR, ALP and γGT until resolution c (frequency at investigator discretion)
> 3 × ULN accompanied by symptoms b	Discontinue the study drug immediately Hospitalize if clinically appropriate Establish causality Complete liver CRF	ALT, AST, TBL, Alb, PT/INR, ALP and γGT until resolution c (frequency at investigator discretion)
> 3 to ≤ 5 × ULN (patient is asymptomatic)	Repeat LFT within the next week If elevation is confirmed, initiate close observation of the patient	Investigator discretion Monitor LFT within 1 to 4 weeks

Criteria	Actions required	Follow-up monitoring
ALP (isolated)		
> 2 × ULN (in the absence of known bone pathology)	Repeat LFT within 48 hours If elevation persists, establish causality Complete liver CRF	Investigator discretion Monitor LFT within 1 to 4 weeks or at next visit
TBL (isolated)		
> 2 × ULN (in the absence of known Gilbert syndrome)	Repeat LFT within 48 hours If elevation persists, discontinue the study drug immediately Hospitalize if clinically appropriate Establish causality Complete liver CRF	ALT, AST, TBL, Alb, PT/INR, ALP and γGT until resolution c (frequency at investigator discretion) Test for hemolysis (e.g. reticulocytes, haptoglobin, unconjugated [indirect] bilirubin)

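### For a confirmed creatinine rise of 50% or more, Table 9-3 asks sites only to consider interrupting study drug, whereas Section 7.1 requires discontinuation; less sharply, Section 9 offers interruptions that 6.3 rules out.

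*Protocol*

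**What the plan says.** Section 7.1 of the protocol lists events for which study treatment must "be discontinued and patients followed up for safety, if possible, if the following occur". One of them is "Major worsening of renal function (e.g. >40% increase from baseline creatinine level").

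Section 9.4 defines a creatinine event as a rise of at least 25%, confirmed after at least 24 hours, "compared to baseline during normal hydration status". It adds that creatinine triggers need follow-up and repeat measurement. Table 9-3 then gives the actions:

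- Rise of 25-49%: "Confirm 25% increase after 24-48h Follow up within 2-5 days". No action on study drug is named.
- Rise of 50% or more: "Follow up within 24-48h if possible Consider drug interruption", with hospitalization or specialized treatment also to be considered.
- Urinary albumin and protein findings: "Consider drug interruption / discontinuation".

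Section 6.3 does not permit dose adjustments or interruptions. Its next sentence says that if an adverse event or any other reason leads to a deviation from the dosing scheme, the sponsor must agree whether the subject continues or is discontinued.

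**The concern.** Sections 7.1 and 9.4 both deal with a percentage rise in creatinine from baseline, but they ask for different things. Section 7.1 is mandatory and permanent. The upper row of Table 9-3 is optional and, on its face, temporary. Table 9-3 itself separates the two actions: its urinary protein entry names both interruption and discontinuation, while the row for 50% or more names interruption alone.

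Table 9-3 is the protocol's list of renal alert actions, so a site facing a raised creatinine is likely to turn to it. A site that follows it literally could pause, or go on dosing, a patient with a confirmed rise of 50% or more whom 7.1 requires to stop. Renal function is a stated safety interest of this trial: 3.6 asks investigators to watch for acute kidney injury, and 7.4 has a renal criterion for putting the study on hold.

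The interruption issue is procedural. A site that pauses an infusion as Section 9 suggests is not told there that 6.3 does not permit interruptions, or that the sponsor must agree before the patient continues.

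**Working it through.** The plan states no figure to reproduce. The check compares thresholds and actions.

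**Step 1: do the two renal rules overlap?** The 7.1 example is a rise above 40%. The upper row of Table 9-3 starts at 50%, and 50 - 40 = 10 percentage points. Every value in that row therefore exceeds the example. As an illustration, assume a baseline creatinine of 1.00 mg/dL. The 7.1 example is passed above 1.00 x 1.40 = 1.40, and the upper row starts at 1.00 x 1.50 = 1.50.

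**Step 2: what does each text direct?**

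| Rise from baseline | Section 7.1 | Table 9-3 | Reading |
|---|---|---|---|
| 25-40% | Example not met | Confirm and follow up | No conflict |
| 41-49%, confirmed | Exceeds the example; judgement remains on whether it is major | Confirm and follow up; no drug action | Gap, not a flat contradiction |
| 50% or more, single value | Major worsening not yet established | Follow up; consider interruption | Arguably compatible |
| 50% or more, confirmed in normal hydration | Must discontinue | Follow up; consider interruption | Conflict |

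**Step 3: does anything join the two texts?** Table 9-3 has 2 creatinine rows. None directs discontinuation, and neither they nor the text of 9.4 refer to 7.1. Section 9.6 says only that stopping criteria appear above, without saying where. The liver rules show the alternative. Section 9.3 refers liver events to 7.1, and Table 9-2 directs discontinuation in 7 of its 11 rows:

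- Immediately, 5 rows: potential Hy's Law; ALT or AST above 8 x ULN; above 3 x ULN with INR above 1.5; above 3 x ULN with symptoms; jaundice.
- If the elevation persists, 2 rows: above 5 to 8 x ULN (for more than 2 weeks), and isolated total bilirubin above 2 x ULN, where the text is "If elevation persists, discontinue the study drug immediately".

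The bilirubin row is a useful model, because it makes the stop depend on a repeat test.

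**Step 4: where is interruption listed or offered despite 6.3?**

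- 9.1, list of responses to an adverse event: 1 (it also lists dose adjustment)
- 9.3, liver laboratory trigger: 1
- Table 9-2, adverse events suggesting liver toxicity: 1
- Table 9-3, creatinine row for 50% or more and urinary protein entry: 2

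Total: 1 + 1 + 1 + 2 = 5. None of the five mentions 6.3 or the sponsor agreement it requires.

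**The case against.** The best defence has four parts.

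- **Table 9-3 handles values that are not yet confirmed.** Its lower row begins with confirmation, its upper row begins with a recheck in 24-48 hours, and 9.4 builds confirmation and normal hydration into the definition of an event. A reader might infer that every value in the upper row contradicts 7.1. The documents do not support that: a single reading in a dehydrated patient can fall in the row without being major renal worsening. This part stands, and it limits the conflict to confirmed rises. It does not remove it, because the row gives no different instruction once the rise is confirmed.
- **The 40% figure is only an example.** A reader might infer that 41-49% is also a straight contradiction. Because 7.1 gives the figure as an illustration, judgement remains near it, so that reading goes too far. The defence is weak from 50%: it is hard to call a confirmed rise of that size less than major when the sponsor's own illustration is above 40%.
- **Section 6.3 already provides a route.** A reader might infer that 6.3 forbids every safety hold outright. Its second sentence sends deviations caused by adverse events to sponsor agreement, and 9.6 has required safety reviews made jointly by sponsor and investigator. This stands in large part. What remains is that the hold still counts as a deviation and that Section 9 does not point to the route.
- **Harm is unlikely.** Infusions are 28 days apart, so a 48-hour recheck will usually be finished before the next one. Section 7.1 also tells investigators to stop treatment they believe is detrimental, and a site holding both texts can apply the stricter one. This is fair and lowers the urgency. It still relies on the site looking up a section that the renal table never mentions.

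**Conclusion.** The concern holds in this form. For a confirmed creatinine rise of 50% or more during normal hydration, 7.1 requires discontinuation and Table 9-3 asks only that interruption be considered, with no cross-reference between them. The whole confirmed range lies at least 10 percentage points above the 7.1 example. This assumes that a confirmed rise of that size counts as major worsening, which follows from the sponsor's own example. For 41-49% the table is silent on study drug, but 7.1 leaves room for judgement.

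The conflict with 6.3 is secondary: five places list or offer an interruption that 6.3 does not permit, softened by the sponsor-agreement route in 6.3 itself.

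This should be fixed because it concerns a patient-safety instruction and the remedy is cheap. The documents give no rate of creatinine rises or of dosing holds, so the number of patients affected cannot be estimated. A reader might infer that mixed handling of these patients would bias the Week 25 QMG comparison; nothing in the documents shows that, and it is not claimed.

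**What to change.** 1. **Table 9-3, row for 50% or more.** Replace the follow-up and interruption text with: *Hold further dosing and repeat within 24-48h; if confirmed during normal hydration, discontinue study treatment as in 7.1.* Keep the hospitalization line. The hold protects the patient while the value is checked, and the condition prevents one unconfirmed reading from ending treatment.
2. **Table 9-3, row for 25-49%.** Add: *A confirmed rise above 40% is assessed under 7.1.* This keeps the judgement that 7.1 allows.
3. **Section 6.3.** Allow safety holds made under Section 9, with sponsor agreement before dosing resumes. Cross-refer to 6.3 from 9.1, 9.3 and Tables 9-2 and 9-3. Remove dose adjustment from the list in 9.1, or mark it not applicable.

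As separate housekeeping, 5.2 says treatment is interrupted after rescue therapy, while Table 5-1, 6.9 and 7.1 say discontinued; the same amendment can align them.

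Cost: wording in one amendment, a letter to sites, and sponsor medical sign-off on the two creatinine rows. No added scheduled visits, staff or patients, and no change to sample size or analysis.

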## 9.5 Pregnancy reporting

To ensure patient safety, each pregnancy in a subject on study drug must be reported to Novartis **within 24 hours** of learning of its occurrence. The pregnancy should be followed up to determine outcome, including spontaneous or voluntary termination, details of the birth, and the presence or absence of any birth defects, congenital abnormalities, or maternal and/or newborn complications. The study drug must be discontinued and the patient should be discontinued. Discontinued pregnant women will complete the EoS visit (Visit 777) assessments as described in the Assessment Schedule (Table 8-1).

Pregnancy must be recorded on a Pharmacovigilance Pregnancy Form and reported by the investigator to the local Novartis Drug Safety and Epidemiology Department. Pregnancy follow-up should be recorded on the same form and should include an assessment of the possible relationship to the Novartis study drug of any pregnancy outcome. Any SAE experienced during pregnancy must be reported on an SAE Report Form.

## 9.6 Early phase safety monitoring

The Investigator will monitor adverse events in an ongoing manner and inform the Sponsor of any clinically relevant observations. Any required safety reviews will be made jointly between medically qualified personnel representing the Sponsor and Investigator. Such evaluations may occur verbally, but the outcome and key discussion points will be

summarized in writing (e-mail) and made available to both Sponsor and all Investigator(s). Criteria pertaining to stopping the study/treatment or adapting the study design are presented above.

When two or more clinical site(s) are participating in the clinical study, the Sponsor will advise the Investigator(s) at all sites in writing (e-mail and by telephone if possible) of any new, clinically relevant safety information reported from another site during the conduct of the study in a timely manner.

## **10 Data review and database management**

### **10.1 Site monitoring**

Before study initiation, at a site initiation visit or at an investigator's meeting, a Novartis representative will review the protocol and CRFs with the investigators and their staff. During the study, Novartis employs several methods of ensuring protocol and GCP compliance and the quality/integrity of the sites' data. The monitor will visit the site to check the completeness of subject records, the accuracy of entries on the CRFs, the adherence to the protocol and to GCP, the progress of enrollment, and to ensure that study drug is being stored, dispensed, and accounted for according to specifications. Key study personnel must be available to assist the monitor during these visits.

The investigator must maintain source documents for each subject in the study, consisting of case and visit notes (hospital or clinic medical records) containing demographic and medical information, laboratory data, electrocardiograms, and the results of any other tests or assessments. All information on CRFs must be traceable to these source documents in the subject's file. The investigator must also keep the original informed consent form signed by the subject (a signed copy is given to the subject).

The investigator must give the monitor access to all relevant source documents to confirm their consistency with the CRF entries. Novartis monitoring standards require full verification for the presence of informed consent, adherence to the eligibility criteria, documentation of SAEs, and the recording of data that will be used for all primary and safety variables. Additional checks of the consistency of the source data with the CRFs are performed according to the study-specific monitoring plan. No information in source documents about the identity of the subjects will be disclosed.

### **10.2 Data collection**

Designated investigator staff will enter the data required by the protocol into the Electronic Case Report Forms (CRF) using fully validated software that conforms to 21 CFR Part 11 requirements. Designated investigator site staff will not be given access to the EDC system until they have been trained. Automatic validation programs check for data discrepancies and, by generating appropriate error messages, allow the data to be confirmed or corrected before transfer of the data to the CRO working on behalf of Novartis. The Investigator must certify that the data entered into the Electronic CRF are complete and accurate. After database lock, the investigator will receive a CD-ROM or paper copies of the subject data for archiving at the investigational site.

All data should be recorded, handled and stored in a way that allows its accurate reporting, interpretation and verification.

The CRO working on behalf of Novartis reviews the data entered into the eCRFs by investigational staff for completeness and accuracy and instruct the site personnel to make any required corrections or additions. Queries are sent to the investigational site using an electronic data query. Designated investigator site staff are required to respond to the query and confirm or correct the data. If the electronic query system is not used, a paper Data Query Form will be faxed to the site. Site personnel will complete and sign the faxed copy and fax it back to the CRO working on behalf of Novartis who will make the correction to the database.

Concomitant medications entered into the database will be coded using the WHO Drug Reference List, which employs the Anatomical Therapeutic Chemical classification system. Medical history/current medical conditions and adverse events will be coded using the Medical dictionary for regulatory activities (MedDRA) terminology.

Laboratory samples will be processed centrally and the results sent electronically to the designated CRO.

At the conclusion of a non-IRT study, the occurrence of any emergency code breaks will be determined after return of all code break reports and unused drug supplies to Novartis.

The occurrence of any protocol deviations will be determined. After these actions have been completed and the database has been declared to be complete and accurate, it will be locked and the treatment codes will be unblinded and made available for data analysis. Any changes to the database after that time can only be made by joint written agreement between the Global Head of Clinical Information Sciences and the Clinical Franchise Head.

### **10.3 Data Monitoring Committee**

A Data Monitoring Committee (DMC) will be instituted. The DMC will be responsible for reviewing the safety results from the interim and final analyses, as well as overseeing the safety data accruing in the trial at regular intervals. It is expected that the DMC will consist of a myasthenia gravis specialist, a neurologist, an immunologist and a statistician.

Details of the working procedures of the DMC are described in the DMC Charter.

### **10.4 Adjudication Committee**

Not required.

## **11 Data analysis**

Analysis of the data will be under the direction of Novartis personnel. Full statistical details will be presented in the Reporting and Analysis Plan (RAP), which will be finalized prior to database lock.

## 11.1 Analysis sets

For all analysis sets, subjects will be analyzed according to the study treatment(s) received.

The full analysis set (FAS) will include all patients who received any study drug.

The safety analysis set will include patients who received any study drug.

The PD analysis set will include all patients who received any study drug and with no protocol deviations with relevant impact on efficacy data.

The PK analysis set will include patients with available PK data and no protocol deviations with relevant impact on PK data.

Patients with non-detectable AChR or MuSK autoantibodies will be excluded from the PD and PK analysis sets.

